6.6.4 Other Allowed Dose Interruptions

If the participant is receiving treatment with lenvatinib and requires surgery during the study, the stop time and restart time of lenvatinib should be as follows:

- For minor procedures: stop lenvatinib at least 2 days before the procedure and restart it at least 2 days after, once there is evidence of adequate healing and no risk of bleeding.
- For major procedures: stop lenvatinib at least 1 week (5 half-lives) prior to surgery and then restart it at least 2 weeks after, once there is evidence of adequate healing and no risk of bleeding.

6.6.5 Second Course Treatment Phase

All participants who have completed the first course may be eligible for up to an additional 9 cycles of pembrolizumab if there is investigator-determined progressive disease by RECIST 1.1 after initial treatment or first course has been completed or stopped for confirmed CR.

Participants may enter the Second Course if all of the following criteria are met:

- The participant received pembrolizumab, determined on unblinding if applicable
- No new anticancer treatment was administered after the last dose of study intervention
- The participant meets all of the inclusion criteria and none of the exclusion criteria
- The study is ongoing

An objective response or disease progression that occurs during the Second Course will not be counted as an event for the primary analysis of either endpoint in this study.

Participants in the Second Course Treatment Phase who continue receiving lenvatinib will be treated at the same dose and frequency of lenvatinib that they were receiving when PD occurred.

6.7 Intervention After the End of the Study

The study is complete upon consent of the last active treatment participant for an extension study using pembrolizumab monotherapy, coformulations, or in combination with a compound (eg, lenvatinib or lenvatinib alone), if available.

All study-related procedures and data collection as defined per protocol will be terminated at study completion. In addition, survival follow-up will be stopped upon study completion as defined in Section 4.4.

6.8 Clinical Supplies Disclosure

This study is open label; therefore, the participant, the study site personnel, the Sponsor, and/or designee are not blinded. Study intervention (name, strength, or potency) is included in the label text; random code/disclosure envelopes or lists are not provided.

7 DISCONTINUATION OF STUDY INTERVENTION AND PARTICIPANT WITHDRAWAL

7.1 Discontinuation of Study Intervention

Discontinuation of study intervention does not represent withdrawal from the study.

As certain data on clinical events beyond study intervention discontinuation may be important to the study, they must be collected through the participant's last scheduled follow-up, even if the participant has discontinued study intervention. Therefore, all participants who discontinue study intervention prior to completion of the protocol-specified treatment period will still continue to be monitored in this study and participate in the study visits and procedures as specified in Section 1.3 and Section 8.10.3 unless the participant has withdrawn from the study (Section 7.2).

Participants may discontinue study intervention at any time for any reason or be discontinued from the study intervention at the discretion of the investigator should any untoward effect occur. In addition, a participant may be discontinued from study intervention by the investigator or the Sponsor if study intervention is inappropriate, the study plan is violated, or for administrative and/or other safety reasons.

A participant must be discontinued from study intervention but continue to be monitored in the study for any of the following reasons:

- The participant or participant's legally acceptable representative requests to discontinue study intervention.
- The participant interrupts pembrolizumab for more than 12 consecutive weeks or lenvatinib for more than 28 consecutive days without prior agreement from the Sponsor.
- The participant has a medical condition or personal circumstance which, in the opinion of the investigator and/or Sponsor, placed the participant at unnecessary risk from continued administration of study intervention.
- The participant has a confirmed positive serum pregnancy test.
- Radiographic disease progression outlined in Section 8.2.1 (exception if the Sponsor approves treatment continuation following confirmed disease progression).
- Any progression or recurrence of any malignancy, or any occurrence of another malignancy that requires active treatment.
- Any study intervention-related toxicity specified as a reason for permanent discontinuation as defined in the guidelines for dose modification due to AEs in Section 6.6.

Completion of pembrolizumab Q6W monotherapy consists of 18 treatments (approximately 2 years). Discontinuation of treatment may be considered for participants who have attained a confirmed CR and have been treated for at least 4 cycles (at least 24 weeks), receiving at least 1 dose of pembrolizumab beyond the date when the initial CR was declared. These participants may be eligible for second course treatment described in Section 6.6.5.

Note: The number of treatments is calculated starting with the first dose. Participants who stop the combination or pembrolizumab after receiving 18 doses may be eligible for retreatment if they progress after stopping study intervention provided they meet the requirements detailed in Section 8.10.3. Participants may be retreated in the Second Course Phase (Retreatment) for up to an additional 9 cycles (approximately 1 year).

7.2 Participant Withdrawal From the Study

A participant must be withdrawn from the study if the participant or participant's legally acceptable representative withdraws consent from the study.

If a participant withdraws from the study, they will no longer receive study intervention or be followed at scheduled protocol visits.

Specific details regarding procedures to be performed at the time of withdrawal from the study are outlined in Section 8.1.9. The procedures to be performed should a participant repeatedly fail to return for scheduled visits and/or if the study site is unable to contact the participant are outlined in Section 7.3.

7.3 Lost to Follow-up

If a participant fails to return to the clinic for a required study visit and/or if the site is unable to contact the participant, the following procedures are to be performed:

- The site must attempt to contact the participant and reschedule the missed visit. If the participant is contacted, the participant should be counseled on the importance of maintaining the protocol-specified visit schedule.
- The investigator or designee must make every effort to regain contact with the participant at each missed visit (eg, telephone calls and/or a certified letter to the participant's last known mailing address or locally equivalent methods). These contact attempts should be documented in the participant's medical record.
- Note: A participant is not considered lost to follow-up until the last scheduled visit for the individual participant. The missing data for the participant will be managed via the prespecified statistical data handling and analysis guidelines.

8 STUDY ASSESSMENTS AND PROCEDURES

- Study procedures and their timing are summarized in the SoA.
- Adherence to the study design requirements, including those specified in the SoA, is essential and required for study conduct.
- The investigator is responsible for ensuring that procedures are conducted by appropriately qualified (by education, training, and experience) staff. Delegation of study site personnel responsibilities will be documented in the Investigator Trial File Binder (or equivalent).
- All study-related medical or dental decisions must be made by an investigator who is a qualified physician (or dentist when appropriate).
- All screening evaluations must be completed and reviewed to confirm that potential participants meet all eligibility criteria. The investigator will maintain a screening log to record details of all participants screened and to confirm eligibility or record reasons for screening failure, as applicable.
- Procedures conducted as part of the participant's routine clinical management (eg, blood count) and obtained before signing of ICF may be utilized for screening or baseline purposes provided the procedure met the protocol-specified criteria and were performed within the time frame defined in the SoA.
- Additional evaluations/testing may be deemed necessary by the investigator and or the Sponsor for reasons related to participant safety. In some cases, such evaluation/testing may be potentially sensitive in nature (eg, HIV, Hepatitis C), and thus local regulations may require that additional informed consent be obtained from the participant. In these cases, such evaluations/testing will be performed in accordance with those regulations.

8.1 Administrative and General Procedures

8.1.1 Informed Consent

The investigator or medically qualified designee (consistent with local requirements) must obtain documented informed consent from each potential participant (or their legally acceptable representative) prior to participating in this clinical study. If there are changes to the participant's status during the study (eg, health or age of majority requirements), the investigator or medically qualified designee must ensure the appropriate documented informed consent is in place.

8.1.1.1 General Informed Consent

Informed consent given by the participant or their legally acceptable representative must be documented on a consent form. The form must include the trial protocol number, trial protocol title, dated signature, and agreement of the participant (or his/her legally acceptable representative) and of the person conducting the consent discussion.

A copy of the signed and dated informed consent form should be given to the participant (or their legally acceptable representative) before participation in the study.

The initial ICF, any subsequent revised ICF, and any written information provided to the participant must receive the IRB/IEC's approval/favorable opinion in advance of use. The participant or his/her legally acceptable representative should be informed in a timely manner if new information becomes available that may be relevant to the participant's willingness to continue participation in the study. The communication of this information will be provided and documented via a revised consent form or addendum to the original consent form that captures the participant's or the participant's legally acceptable representative's dated signature.

If the investigator recommends continuation of study intervention beyond disease progression, the participant or their legally acceptable representative will be asked to provide documented informed consent.

Specifics about the study and the study population are to be included in the study informed consent form.

Informed consent will adhere to IRB/IEC requirements, applicable laws and regulations, and Sponsor requirements.

8.1.2 Inclusion/Exclusion Criteria

All inclusion and exclusion criteria will be reviewed by the investigator, who is a qualified physician, to ensure that the participant qualifies for the study.

8.1.3 Participant Identification Card

All participants will be given a participant identification card identifying them as participants in a research study. The card will contain study site contact information (including direct telephone numbers) to be used in the event of an emergency. The investigator or qualified designee will provide the participant with a participant identification card immediately after the participant provides documented informed consent. At the time of intervention allocation, site personnel will add the treatment/randomization number to the participant identification card.

The participant identification card also contains contact information for the emergency unblinding call center so that a healthcare provider can obtain information about study intervention in emergency situations where the investigator is not available.

8.1.4 Medical History

A medical history will be obtained by the investigator or qualified designee. The medical history will collect all active conditions and any condition diagnosed within the prior 10 years that the investigator considers to be clinically significant. Details regarding the disease for which the participant has enrolled in this study will be recorded separately and not listed as medical history.

8.1.5 Prior and Concomitant Medications Review

8.1.5.1 Prior Medications

The investigator or qualified designee will review prior medication use, including any protocol-specified washout requirement, and record prior medication taken by the participant within 28 days before the first dose of study intervention.

8.1.5.2 Concomitant Medications

The investigator or qualified designee will record medication, if any, taken by the participant during the study through the Safety Follow-up visit. In addition, new medications started during the Second Course Treatment Phase through the Second Course Safety Follow-up visit should be recorded. Concomitant medications administered >30 days after the last dose of study intervention will be recorded for SAEs and ECIs as defined in Section 8.4.1. In the posttreatment follow-up period, information about new anticancer therapies will be collected.

8.1.6 Assignment of Screening Number

All consented participants will be given a unique screening number that will be used to identify the participant for all procedures that occur prior to intervention allocation. Each participant will be assigned only 1 screening number. Screening numbers must not be re-used for different participants.

Any participant who is screened multiple times will retain the original screening number assigned at the initial screening visit. Specific details on the screening/rescreening visit are provided in Section 8.10.1.

8.1.7 Assignment of Treatment/Randomization Number

All eligible participants will be allocated, by nonrandom assignment, and will receive a treatment/randomization number. The treatment/randomization number identifies the participant for all procedures occurring after treatment allocation. Once a treatment/randomization number is assigned to a participant, it can never be reassigned to another participant.

A single participant cannot be assigned more than 1 treatment/randomization number.

8.1.8 Study Intervention Administration

The first dose of study intervention should begin as close as possible to the date of allocation but can occur up to 3 days following allocation. Every effort should be made to ensure the participants receive the first dose of study intervention on the date of allocation. Study interventions will be administered by the investigator and/or qualified study staff according to the specifications in the Pharmacy Manual.

8.1.8.1 Timing of Dose Administration

8.1.8.1.1 Lenvatinib

Participants should be given clear instructions on how and when to take their study intervention. Lenvatinib will be taken orally QD, with doses taken at approximately the same time of day. Lenvatinib may be administered at home except on days when clinic visits are scheduled to occur. Study intervention on these days will occur in the clinic after completion of all other assessments.

If a dose is missed and cannot be taken within 12 hours, study participants should skip that dose and take the next dose at the usual time of administration. Participants who vomit after study drug administration should not retake that study drug dose but should resume taking study drug with the next scheduled dose. Lenvatinib can be taken without regard to food.

8.1.8.1.2 Pembrolizumab

Study treatment with pembrolizumab should be administered on Day 1 of each cycle after all procedures/assessments have been completed as detailed in the SoA (Section 1.3). All study treatments will be administered on an outpatient basis. Pembrolizumab may be administered up to 3 days before or after the scheduled Day 1 of each cycle due to administrative reasons except for C1D1, where the window is +3 days from allocation.

Pembrolizumab will be administered using a 30-minute IV infusion. Sites should make every effort to target infusion timing to be as close to 30 minutes as possible. However, given the variability of infusion pumps from site to site, a window of -5 minutes and +10 minutes is permitted (ie, infusion time is 30 minutes -5 min/+10 min).

The Pharmacy Manual contains specific instructions for preparation of the infusion fluid and administration.

8.1.9 Discontinuation and Withdrawal

Participants who discontinue study intervention prior to completion of the treatment period should be encouraged to continue to be followed for all remaining study visits as outlined in the SoA and Section 8.10.3.

Participants who withdraw from the study should be encouraged to complete all applicable activities scheduled for the final study visit at the time of withdrawal. Any AEs that are

present at the time of withdrawal should be followed in accordance with the safety requirements outlined in Section 8.4.

8.1.10 Participant Blinding/Unblinding

This is an open-label study; there is no blinding for this study.

8.1.11 Calibration of Equipment

The investigator or qualified designee has the responsibility to ensure that any device or instrument used for a clinical evaluation/test during a clinical study that provides information about inclusion/exclusion criteria and/or safety or efficacy parameters shall be suitably calibrated and/or maintained to ensure that the data obtained are reliable and/or reproducible. Documentation of equipment calibration must be retained as source documentation at the study site.

8.1.12 Tumor Tissue Collection

During the screening period, a tissue sample is required for each participant consisting of:

- A newly obtained core or incisional biopsy of a tumor lesion, which was not previously irradiated
- OR
- An archival tumor tissue sample if a new biopsy is unavailable.

FFPE tissue blocks are preferred to slides. Newly obtained biopsies are preferred to archived tissue.

Newly cut unstained slides must be submitted to the central laboratory within 14 days of cut date (details pertaining to tumor tissue submission can be found in the Procedures Manual).

The central laboratory will provide consultative review to confirm nccRCC histology without any admixed clear cell component.

8.2 Efficacy Assessments

8.2.1 Tumor Imaging and Assessment of Disease

In addition to survival, efficacy will be assessed based on imaging evaluation of changes in tumor burden over time, until the participant is discontinued from the study or goes into survival follow-up. The process for image collection and transmission to the iCRO can be found in the SIM. Tumor imaging is strongly preferred to be acquired by CT. For the abdomen and pelvis, contrast-enhanced MRI may be used when CT with iodinated contrast is contraindicated, or when mandated by local practice. The same imaging technique should be used in a participant throughout the study to optimize the reproducibility of the assessment of

existing and new tumor burden and improve the accuracy of the response assessment based on imaging. Note: for the purposes of assessing tumor imaging, the term “investigator” refers to the local investigator at the site and/or the radiological reviewer at the site or at an offsite facility.

If brain imaging is performed, MRI is preferred; however, CT imaging will be acceptable, if MRI is medically contraindicated.

Bone scans may be performed to evaluate bone metastases. Any supplemental imaging done to support a positive or negative bone scan, such as plain X-rays acquired for correlation, should be submitted to the iCRO.

Other types of medical imaging (such as ultrasound) should not be submitted to the iCRO, and will not be included in response assessment.

Expedited confirmation of measurable disease based on RECIST 1.1 by BICR at screening will be used to determine participant eligibility. Confirmation by BICR that the participant’s imaging shows at least 1 lesion that is appropriate for selection as a target lesion per RECIST 1.1 is required before participant allocation.

All scheduled imaging for all study participants will be submitted to the iCRO. In addition, imaging that is obtained at an unscheduled time point, for any reason (including suspicion of progression or other clinical reason), should also be submitted to the iCRO if it shows progression, or if it is used to support a response assessment. All imaging acquired within the protocol-specified window of time around a scheduled imaging visit can be classified as pertaining to that visit.

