Imaging assessments will include chest CT and abdomen and pelvis CT/MRI throughout the study. Bone scans will be performed at screening and will only be repeated throughout the study if a participant has a positive result at screening. Brain imaging at screening is only required for participants with previously documented brain metastases. On-study brain imaging will only be performed as clinically indicated or to confirm CR in a participant with brain lesions at baseline. All imaging obtained will be submitted to the iCRO for BICR, which will assess the images per RECIST 1.1, adjusted to allow for a maximum of 10 total target lesions and a maximum of 5 target lesions per organ. However, all decisions to

discontinue study intervention(s) due to disease progression are based solely on the site radiology's assessment.

Adverse event monitoring will be ongoing throughout the study. AEs will be graded in severity according to the guidelines outlined in the NCI CTCAE Version 5.0.

During both Initial Treatment Phase and the Second Course Treatment Phase, if pembrolizumab is discontinued because of toxicity, lenvatinib alone may be continued based on physician discretion regarding the benefits of continuing VEGFR-based oral monotherapy. If lenvatinib is discontinued due to toxicity, pembrolizumab alone may be continued.

Specific procedures to be performed during the study, as well as their prescribed times and associated visit windows, are outlined in the SoA in Section 1.3. Details of each procedure are provided in Section 8.

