8.2.1.2 Tumor Imaging During the Study

The first on-study imaging assessment should be performed at 12 weeks ([84 days \pm 7 days]) from the date of allocation. Subsequent tumor imaging should be performed every 6 weeks

(42 days \pm 7 days) or more frequently if clinically indicated. After 54 weeks (378 days \pm 7 days)], participants who remain on treatment will have imaging performed every 12 weeks (84 days \pm 7 days). Imaging timing should follow calendar days and should not be adjusted for delays in cycle starts. Imaging should continue to be performed until disease progression is identified by the investigator, the start of new anticancer treatment, withdrawal of consent, or death, or notification by the Sponsor, whichever occurs first. All supplemental imaging must be submitted to the iCRO.

Objective response should be confirmed by a repeat imaging assessment. Tumor imaging to confirm PR or CR should be performed at least 4 weeks after the first indication of a response is observed. Participants will then return to regular scheduled imaging, starting with the next scheduled imaging time point. Participants who receive additional imaging for confirmation do not need to undergo the next scheduled tumor imaging if it is less than 4 weeks later; tumor imaging may resume at the subsequent scheduled imaging time point. Note: Response does not typically need to be verified in real time by the BICR.

On-study brain or bone imaging should be performed if clinically indicated or to confirm CR (if other lesions indicate CR and brain or bone lesions existed at baseline).

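### Section 8.2.1 lets the site's judgment decide which unscheduled scans reach central review, while Section 4.1 sends all imaging; the two rules must be reconciled

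*Combined protocol and SAP*

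**What the plan says.** The combined protocol and SAP states the submission rule in three places.

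- Section 4.1 (Overall Design): "All imaging obtained will be submitted to the iCRO for BICR, which will assess the images per RECIST 1.1". No condition is attached.
- Section 8.2.1 (Tumor Imaging and Assessment of Disease) splits the rule. For scheduled scans: "All scheduled imaging for all study participants will be submitted to the iCRO". An unscheduled scan, whatever the reason for it, "should also be submitted to the iCRO if it shows progression, or if it is used to support a response assessment". The section adds: "All imaging acquired within the protocol-specified window of time around a scheduled imaging visit can be classified as pertaining to that visit".
- Section 8.2.1.2 (Tumor Imaging During the Study): "All supplemental imaging must be submitted to the iCRO". The term supplemental is not defined there.

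Unscheduled scans are foreseen, since Section 8.2.1.2 allows imaging "or more frequently if clinically indicated". For imaging purposes, Section 8.2.1 says that the term investigator "refers to the local investigator at the site and/or the radiological reviewer at the site or at an offsite facility".

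ORR, DOR and PFS are all based on BICR (Sections 9.1 and 9.4.1, Table 12). PFS progression is dated to the first assessment at which BICR documents it (Section 9.6.1.3). Section 4.2.1.1 gives reduction of bias in response assessment as the reason for central review.

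**The concern.** The trial is open-label with one arm, and its radiological endpoints rest on a central read that is meant not to depend on the site's opinion. Section 8.2.1 makes one class of image available to that read only after the site has formed an opinion. The scan most affected is one taken because progression was suspected and then read locally as not showing it. Disagreement between site and central reader matters most on such a scan, and it need not be sent.

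Two things are at stake. BICR progression dates, which drive PFS and DOR, can be late or missing. Sites that follow different sections of the same protocol can also send different sets of images.

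**Working it through.** **1. The rules side by side**

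| Imaging | Section 4.1 | Section 8.2.1 | Section 8.2.1.2 |
|---|---|---|---|
| Scheduled | sent | sent | not separately stated |
| Unscheduled, in window | sent | can be assigned to the scheduled visit, so sent | sent if supplemental |
| Unscheduled, out of window, site sees progression | sent | sent | sent if supplemental |
| Unscheduled, out of window, used for a response assessment (includes confirmation scans) | sent | sent | sent if supplemental |
| Unscheduled, out of window, site sees no progression and does not use it | sent | **not required** | sent if supplemental |

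The first two columns conflict only in the last row. Before submission only the site can have read the scan, so both conditions in 8.2.1 turn on the site's judgment.

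**2. Effect on a progression date**

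Inputs from Section 8.2.1.2: first scan at 84 ± 7 days from allocation, then every 42 ± 7 days to Week 54, then every 84 ± 7 days. If BICR would have called progression on an unsubmitted scan, the date moves to the next submitted scan. The nominal upper bound is the scan interval:

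- before Week 12: 84 days, or 12 weeks (84 + 7 = 91 days if the first scan is at the end of its window);
- Weeks 12 to 54: 42 days, or 6 weeks (42 / 30.4375 = 1.4 months);
- after Week 54: 84 days, or 12 weeks (84 / 30.4375 = 2.8 months).

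The windows do not enlarge the last two. The earliest out-of-window scan is 8 days after a nominal visit date, and the next scheduled scan is at most 7 days late. That gives 42 − 8 + 7 = 41 days and 84 − 8 + 7 = 83 days.

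**3. How an event can be lost**

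- Section 8.2.1.3 waives the end-of-treatment scan if imaging was done in the 4 weeks before discontinuation. It does not require that imaging to have been submitted.
- If new anticancer therapy starts before another submitted scan, the primary PFS analysis censors at the most recent assessment preceding that therapy (Table 11). Table 10 does the same for DOR.
- A progression visible to BICR only on the unsubmitted scan then becomes a censored observation.

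The PFS sensitivity analyses cover part of this. Sensitivity Analysis 1 would count a later documented progression or death. Sensitivity Analysis 2 would count the start of new therapy as progression in a participant with no documented progression or death. Neither recovers the image, and no alternative censoring is planned for DOR.

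**4. Scale for ORR**

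Table 13 was reproduced first. Clopper-Pearson limits are the beta quantiles B(0.025; x, n − x + 1) and B(0.975; x + 1, n − x), with n = 152. For x = 53, 61, 64 and 68 they give (27.3, 43.0), (32.3, 48.4), (34.2, 50.4) and (36.7, 53.0), which match the plan.

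One participant is 1/152 = 0.66 percentage points. Purely as an assumed range, 1 to 5 fewer responders than 61 moves 40.1% (32.3, 48.4) to between 39.5% (31.6, 47.7) and 36.8% (29.2, 45.0). Nothing in the documents supports a count in that range.

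An ORR effect needs several things together: an out-of-window scan between first response and confirmation, not read by the site as progression and not used; a central read that would have ended the response; and a later submitted scan on which BICR still confirms it.

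**The case against.** The strongest reply is that this is a difference of wording with little effect. Section 4.1 is an overview that refers to Section 8 for procedural detail. The transmission process is in the imaging manual, which is not among the documents. If supplemental imaging in 8.2.1.2 covers unscheduled scans, the plan already requires what is asked for here. Dating progression at the next scan is also the ordinary limit of periodic assessment, which Section 9.6.1.3 acknowledges.

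Much of this stands as a limit on size. It does not remove the conflict. Sections 4.1 and 8.2.1 cannot both be followed for the scans in the last row of the table. The word supplemental may cover only supporting images, such as the X-rays that 8.2.1 mentions alongside bone scans, so 8.2.1.2 neither settles the matter nor clearly adds a second contradiction. The ordinary interval limit concerns scans not taken; here the scan exists.

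A reader might infer more than the documents support:

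- *That every unscheduled scan read as stable is withheld.* The second condition covers use in a response assessment, which can include an assessment of stable disease. Nothing tells sites to hold such scans back.
- *That the review is not really blinded.* Readers can remain blinded to the site's opinion. The weakness is in which images they receive.
- *That the rule favours the treatment overall.* Scans on which the site sees progression are also sent, and these give BICR earlier chances to call it. Neither scan frequency nor site-to-central disagreement is given, so the net direction cannot be shown.
- *That central review is the only safeguard.* Responses need a confirmatory scan at least 4 weeks later, and PFS has a sensitivity analysis on the investigator's assessment.

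**Conclusion.** The conflict between Sections 4.1 and 8.2.1 is real and unresolved in the documents, and it should be corrected. For a participant with an unsubmitted scan on which BICR would have called progression, the date can only be delayed or lost. The delay is nominally up to 12 weeks before Week 12, up to 6 weeks in Weeks 12 to 54, and up to 12 weeks after Week 54. Loss requires that the scan replaced the end-of-treatment scan and that new therapy began before another submitted scan.

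The exposure is mainly to BICR-based PFS and DOR. An inflated ORR is not a supported conclusion: scheduled and confirmation scans reach BICR, in-window scans can count as scheduled, and the route to an effect is remote. No stated figure in the plan changes.

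This rests on sites following 8.2.1 as written and on some unscheduled, out-of-window scans being neither read as progression nor used. Their number is not given, so the net effect cannot be computed.

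**What to change.** In Section 8.2.1, replace the condition with the rule that Section 4.1 already states. All CT, MRI and bone imaging obtained up to the end of efficacy follow-up, scheduled or unscheduled, is submitted to the iCRO and read by BICR whatever the local result. Keep the existing exclusion of modalities such as ultrasound. State in Section 8.2.1.2 whether supplemental imaging includes unscheduled scans, and align the imaging manual.

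Ask sites for unsubmitted scans already taken, where available, so that one rule applies to all participants at the final analysis. Report how many unscheduled scans were obtained, how many had not been submitted, and how many BICR progression dates changed once they were read.

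The cost is a short text change, a note to sites, and extra image transfers and central reads. At Amendment 04, with some analyses already performed, this includes retrospective retrieval, which may be incomplete. No participant undergoes any new procedure.
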